### 5.3.3. Key Efficacy Measures

**A migraine day** is defined as any calendar day on which a headache occurs which meets criteria A, B, and C OR meets criteria D and E, as listed below, as per participant eDiary. Calendar days begin at midnight and last until 11:59 PM (23:59).

- A. Headache has at least two of the following four characteristics:
  - i. Unilateral location
  - ii. Pulsating quality
  - iii. Moderate or severe pain intensity
  - iv. Aggravated by or causing avoidance of routine physical activity (e.g., walking or climbing stairs)
- B. At least one of the following:
  - i. Nausea and/or vomiting
  - ii. Photophobia and phonophobia
  - iii. Typical aura (i.e., visual, sensory, or speech/language) accompanying or within 60 minutes before headache begins
- C. Duration of headache lasting 2 hours or longer on a calendar day unless an acute, migraine-specific medication (i.e., triptan or ergot derivative) was used after the start of the headache, in which case no minimum duration will be specified.

OR

- D. Any headache which fulfills one criterion from (1) and at least one criterion from (2) OR fulfills at least two criteria from (1) and no criteria from (2).
  - 1) Headache characteristics:
    - i. Unilateral location
    - ii. Pulsating quality
    - iii. Moderate or severe pain intensity
    - iv. Aggravated by or causing avoidance of routine physical activity (e.g., walking or climbing stairs)
  - 2) Symptoms:
    - i. Nausea and/or vomiting
    - ii. Photophobia and phonophobia
    - iii. Typical aura (i.e., visual, sensory, or speech/language) accompanying or within 60 minutes before headache begins
- E. Duration of headache lasting 2 hours or longer on a calendar day unless an acute, migraine-specific medication (i.e., triptan or ergot derivative) was used after the start of the headache, in which case no minimum duration will be specified.

**A headache day** is defined as any calendar day on which headache pain lasting 2 hours or longer occurs unless an acute headache medication (e.g., ibuprofen, triptan) was used after the start of the headache, in which case no minimum duration will be specified. Note that antiemetics will

not be counted as an acute headache medication for headache day identification. Calendar days begin at midnight and last until 11:59 PM (23:59).

**An acute medication use day** is defined as any day on which a participant reports, per eDiary, the intake of allowed medication(s) to treat an acute migraine. The allowed medications include the following categories of drugs: triptans, ergots, opioids, analgesics (including acetaminophen), NSAIDs (including aspirin), and antiemetics.

**A triptan use day** is defined as any day on which a participant reports intake of a triptan to treat a migraine per eDiary.

Headache day pain intensity is defined as the worst pain intensity on any headache day where headache pain intensity will be subjectively rated by the patient on a scale from mild to severe:

- Mild pain ( 1)
- Moderate pain ( 2)
- Severe pain ( 3)

If participants experience no headache in a day, then the corresponding pain intensity of that day will be set as missing.

#### **5.3.4. Health Outcome Measures**

##### **5.3.4.1. HIT-6**

The HIT-6 is a 6-question assessment used to measure the impact headaches have on a participant's ability to function on the job, at school, at home, and in social situations. It assesses the effect that headaches have on normal daily life and the participant's ability to function. Responses are based on frequency using a 5-point scale ranging from "never" to "always." The HIT-6 total score, which ranges from 36 to 78, is the sum of the responses each of which is assigned a score ranging from 6 points (never) to 13 points (always).

##### **5.3.4.2. Migraine Disability Assessment (MIDAS)**

The MIDAS is a 7-item questionnaire designed to quantify headache-related disability over a 3-month period. The MIDAS score is the sum of missed work or school days, missed household work days, days at work or school plus days of household work where productivity was reduced by half or more, and missed non-work activity days due to headaches in the last 3 months.

#### **5.3.4.3. Patient Global Impression of Change (PGIC)**

The PGIC is a single item questionnaire used to measure the participant's impression of overall change in migraine since the first dose of study medication. The measure uses a 7-point rating scale with responses ranging from "very much better" to "very much worse."

#### **5.3.4.4. Work Productivity and Activity Impairment Questionnaire: Migraine V2.0 (WPAI:MIGRAINE)**

The WPAI:MIGRAINE will be used to assess work productivity specific to migraine. The measure uses a one-week recall and contains six questions related to work productivity. The WPAI measures both presenteeism and absenteeism. The measure yields four scores expressed as impairment percentages ranging from 0 to 100%: Percent work time missed, percent impairment while working, percent overall work impairment, and percent activity impairment due to migraine.

#### **5.3.4.5. European Quality of Life - 5 Dimensional (EQ-5D-5L)**

EQ-5D-5L is a generic instrument for use as a measure of health status. As of 2009, the European Quality of Life - 5 Dimension - 5-Level (EQ-5D-5L) has also been available for use; this version was developed to improve the sensitivity of the instrument and to reduce ceiling effects ([The EuroQol Group, 2020](#)). The EQ-5D-5L consists of 2 components - the EQ-5D descriptive system and the EQ VAS. The descriptive system comprises 5 dimensions (mobility, self-care, usual activities, pain/discomfort, anxiety/depression). The mobility dimension queries the participant's walking ability. The self-care dimension queries the participant's ability to wash or dress by himself. The usual activities dimension assesses the participant's performance in "work, study, housework, family or leisure activities." The pain/discomfort dimension measures how much pain or discomfort a participant has. The anxiety/depression dimension assesses how anxious or depressed a participant is. The respondent is asked to indicate his/her health state by ticking (or placing a cross) in the box against the most appropriate statement in each of the 5 dimensions. The scoring range of the EQ-5D descriptive system is typically from 0 (dead) to 1 (full health). The EQ VAS records the respondent's self-rated health on a vertical, visual analogue scale where the endpoints are labeled "Best imaginable health state" and "Worst imaginable health state." The scoring range of the EQ VAS is from 0 (worst imaginable health) to 100 (best imaginable health).

#### **5.3.4.6. Patient Global Impression – Severity (PGI-S)**

The PGI-S is a single item questionnaire used to measure the participant's impression of severity in relation to migraine symptoms overall at the time of administration of the measure. The measure uses a 5-point rating scale with responses ranging from "none" to "very severe."

#### **5.3.4.7. Patient Satisfaction with Study Medication**

Overall satisfaction with the study medication for prevention of migraine will be assessed using a single item and a 7-point rating scale, ranging from extremely satisfied (0) to extremely dissatisfied (6).

#### **5.3.4.8. Activity Impairment in Migraine – Diary (AIM-D)**

The AIM-D is an 11-item daily diary measure that assesses the impact of migraine and is comprised of two domains that evaluate performance of daily activities (7 items) and physical impairment (4 items). Participants are asked to rate the level of difficulty experienced in the past 24 hours with performance of daily activities (i.e., difficulty with household chores, errands, leisure activities at home, leisure or social activities outside the home, strenuous physical activities, concentrating, and thinking clearly) and physical impairment (i.e., difficulty walking, moving body, bending forward, and moving head) using a 6-point rating scale ranging from "Not difficult at all," "A little difficult," "Somewhat difficult," "Very difficult," "Extremely difficult," and "I could not do it at all." Three items include a response of "I did not...," for example, "I did not have errands planned." The AIM-D was developed as an electronic daily diary with the same set of questions administered in headache and non-headache versions. The Headache version is administered on days when a participant reports a headache and the Non-Headache version is administered on days when a participant does not report having a headache. The AIM-D instructs participants to answer each question based on the level of difficulty experienced in the past 24 hours for both versions, with "during your headache" indicated for the AIM-D Headache version. In addition to the two domain scores, a total score using all 11 items can also be calculated. Each raw daily domain score, as well as the raw daily total score, are transformed to a 0-100 scale, with higher scores indicating greater impact of migraine (i.e., higher disease burden).

#### **5.3.4.9. Activity Level and Activity Limitation**

Two items based on a 24-hour recall will be administered daily using Headache and Non-headache versions as additional health outcome measures and for evaluation of the AIM-D. The first item will be used to assess activity level within the past 24 hours with a 5-level response scale ranging from "No activity Spent all day lying down" to "Exercised Brisk walk, running, jogging, biking, or other activity for 30 or more minutes." The second item will be used to evaluate activity limitation with a 5-level response scale ranging from "Not at all limited I could do everything" to "Extremely limited."

### 5.3.4.10. Migraine Specific Quality of Life Questionnaire, Version 2.1 (MSQ v2.1)

The MSQ v2.1 is a 14-item questionnaire designed to measure health-related quality-of-life impairments attributed to migraine in the past 4 weeks. It is divided into three domains: Role Function Restrictive assesses how migraines limit one's daily social and work-related activities; Role Function Preventive assesses how migraines prevent these activities; and the Emotional Function domain assesses the emotions associated with migraines. Participants respond to items using a 6-point scale ranging from "none of the time" to "all of the time." Raw dimension scores are computed as a sum of item responses and rescaled to a 0 to 100 scale, where higher scores indicate better quality of life.

The detailed algorithms for derivation of the above health outcome measures are presented in Section 6.4.3.

## 5.4. Safety Analyses

The safety analysis will be performed using descriptive statistics as described in Section 5.1 based upon the Safety population.

### 5.4.1. Extent of Exposure

The study will consist of a 52-week treatment period and a 4-week safety follow up period; total study duration is 56 weeks.

Exposure to extension study treatment for the Safety population during the open-label treatment period will be summarized for treatment duration, calculated as the number of days from the date of the first dose of extension study treatment to the date of the last dose taken, inclusive.

The number and percentage of participants with each treatment duration of  $\geq 1$  day,  $\geq 28$  days,  $\geq 56$  days,  $\geq 84$  days,  $\geq 90$  days,  $\geq 112$  days,  $\geq 140$  days,  $\geq 168$  days,  $\geq 180$  days,  $\geq 196$  days,  $\geq 224$  days,  $\geq 252$  days,  $\geq 270$  days,  $\geq 280$  days, and  $\geq 360$  will be summarized.

Participant-years, defined as exposure to the study treatment in years, will be summarized for the Safety population.

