4.1 Number of Participants

All participants who either complete Study 3101-303-002 or are newly recruited and complete the screening/baseline period, and meet all eligibility requirements, may participate in this study. At least 170 participants will be enrolled at approximately 25 centers in Japan, to meet a target of a minimum of 100 participants at 1 year. A minimum of 30 participants enrolled (at selected sites only) must be classified as De Novo EM Participants (see definition below).

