### 3. Sample Size Determination

The study sample size was driven by regulatory safety requirements for the duration and number of participants exposed rather than statistical considerations. At least 170 participants will be enrolled into this long-term, open label, safety extension study including at least 140 participants from the lead-in study (Study 3101-303-002) and approximately 30 De Novo EM Participants (from selected sites only) to meet a target of a minimum of 100 participants exposed to atogepant at 1 year.

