#### **5.4.3. Adverse Events**

Adverse events (AEs) will be coded using the Medical Dictionary for Regulatory Activities (MedDRA) version 27.0 or higher.

An AE will be considered as a treatment-emergent adverse event (TEAE) if the AE began or worsened (increased in severity or became serious) on or after the date of the first dose of open-label study treatment. An AE that occurs more than 30 days after the last dose of open-label study treatment or the safety follow-up visit (Visit 15) in this extension study whichever comes later will not be counted as a TEAE. Per case report form instructions, a new AE record will be created for any AE that worsens; therefore, TEAEs can be identified as those AEs captured in Study 3101-306-002 with recorded onset date on or after the date of the first dose of open-label study treatment and within 30 days after the last dose of open-label study treatment or Visit 15 whichever comes later.

An AE is a TESAE if it is a TEAE that additionally meets any SAE criterion below (as specified in the protocol Section 9.1.2):

- Results in death
- Is life threatening
- Requires inpatient hospitalization or prolongation of existing hospitalization
- Results in persistent disability/incapacity
- Is a congenital anomaly/birth defect
- Other situations that the medical or scientific judgment considers to be serious.

TEAEs that started after the date of last dose of open-label study treatment will be considered as newly emergent TEAEs (NEAEs).

TEAEs that started on or after the date of first dose of open-label study treatment will be summarized.

Overall summary of AEs will be provided on a per-participant basis for categories of TEAEs, treatment-related TEAEs, TESAEs, treatment-related TESAEs, TEAEs leading to study intervention discontinuation, and deaths.

The number and percentage of participants reporting TEAEs will be tabulated by system organ class (SOC) and preferred term (PT), and further categorized by severity. If more than 1 AE is coded to the same preferred term for the same participants, the participant will be counted only once for that preferred term using the greatest severity for the summarization by severity.

The number and percentage of participants reporting treatment-related TEAEs will be tabulated by SOC and PT.

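### TEAEs are reported only as crude percentages of everyone treated; adding rates per participant-year at risk would be a cheap improvement for the 52-week safety objective

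*SAP*

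**What the plan says.** Safety and tolerability over 52 weeks is the primary objective (SAP 1.1 and 2), and SAP 5.4 makes the safety analysis descriptive, on the Safety population.

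- **Adverse events (SAP 5.4.3).** "The number and percentage of participants reporting TEAEs will be tabulated by system organ class (SOC) and preferred term (PT". Treatment-related TEAEs, TESAEs, newly emergent AEs and TEAEs leading to discontinuation are handled the same way.
- **Counting window (SAP 5.4.3).** "An AE that occurs more than 30 days after the last dose of open-label study treatment", or after Visit 15 if that is later, is not a TEAE.
- **Timing (SAP 5.4.3).** One table splits treatment-related TEAEs by onset interval, again as number and percentage. No denominator is defined for the later intervals.
- **Exposure (SAP 5.4.1).** "Participant-years, defined as exposure to the study treatment in years, will be summarized for the Safety population". Duration runs from first to last dose.
- **Cohorts (SAP 5.5.1).** All safety endpoints are shown for 3101-303-002 Completers, De Novo EM Participants and overall.
- **Size (SAP 3).** "At least 170 participants will be enrolled into this long-term, open label, safety extension study", "to meet a target of a minimum of 100 participants exposed to atogepant at 1 year". The number was "driven by regulatory safety requirements for the duration and number of participants exposed rather than statistical considerations".

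Neither document plans an exposure-adjusted rate, a cumulative-incidence estimate or a confidence interval for an AE result.

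**The concern.** A participant who leaves in week 3 counts in the denominator exactly as one who completes 52 weeks. If some participants leave early and their risk would have continued, the percentage falls below the one-year risk under continued treatment. It also depends on how long people stayed, so two cohorts with equal event rates but unequal retention will show different percentages.

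The protocol leaves room for unequal early exposure. Completers are dispensed drug at Visit 1 (Protocol 8.4.2.1), and Protocol 8.9 lists Visit 1 laboratory, serology, drug-screen and ECG findings that require their withdrawal. De Novo participants have the corresponding checks at Visit -1. How many Completers would be dosed and then withdrawn on a returned result is not knowable from the documents.

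At stake is how the primary safety results read against the 52-week objective, and which preferred terms reach the 5% common-TEAE table.

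**Working it through.** **Inputs from the documents.** At least 170 enrolled and a minimum of 100 at one year (SAP 3); 52 weeks of treatment plus 4 weeks of follow-up (SAP 5.4.1); TEAE window of 30 days after last dose or Visit 15, whichever is later (SAP 5.4.3).

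**Assumptions, not in the documents.** True one-year risk of 10%; constant event and dropout hazards; retention of 59%, 75% and 85%.

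**The plan's own figure.** No dropout rate is given, so 170 cannot be reproduced. Inflating 100 by 1/(1 − d) gives 112, 125, 134, 143 and 167 for d = 10%, 20%, 25%, 30% and 40%. Solving backwards, d = 70/170 = 41.2%, or 59% retention. That is the largest loss compatible with both minimums, not a forecast.

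**Step 1: no events after last dose.** With λ = −ln(0.90) = 0.1054 and δ = −ln(retention), the expected crude proportion is

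C₀ = λ/(λ+δ) × [1 − exp(−(λ+δ))].

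At 59% retention δ = 0.5306, so C₀ = 0.1657 × 0.4706 = 7.8%.

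**Step 2: same hazard through the 30-day window.** Everyone, including completers, gains τ = 30/365 year, so

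C₁ = 1 − exp(−λτ) × (1 − C₀), with exp(−λτ) = 0.9914.

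At 59% retention C₁ = 1 − 0.9914 × 0.9220 = 8.6%.

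| Retention | C₀ | C₁ | Relative shortfall against 10% |
|---|---|---|---|
| 59% | 7.8% | 8.6% | 22% to 14% |
| 75% | 8.7% | 9.5% | 13% to 5% |
| 85% | 9.2% | 10.0% | 8% to 0% |

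A lower off-drug hazard falls between the two columns. At 90% retention C₁ is 10.3%, slightly above the true value, because completers are counted past week 52.

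**Step 3: timing, at 41.2% loss.** These figures stop observation at one year and are given without and then with the tail. If all dropout falls in the last 12 weeks, 10% appears as 9.6% or 9.8%. If it all falls by week 12, 10% appears as 6.4% or 6.7%. If every event occurs in the first 4 weeks, a true 5% appears as 4.9%.

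**Step 4: the 5% cut.** A true 5% at 59% retention gives C₀ = 3.9% and C₁ = 4.3%, both below the threshold in expectation. SAP 5.4.3 applies that threshold within each cohort.

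**Step 5: does a rate recover the risk?** At 59% retention with no tail, 170 × 7.8% = 13.25 participants with an event over 125.8 participant-years to first event or exit. The rate is 10.5 per 100, and 1 − exp(−0.1054) = 10%.

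**Step 6: why the SAP 5.4.1 participant-years will not do.** In the same scenario, total first-to-last-dose time is 170 × 0.776 = 131.9 years. With post-dose events counted, the numerator is 170 × 8.59% = 14.6, giving 11.1 per 100 instead of 10.5. Numerator and denominator cover different periods.

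**Step 7: precision in the small cohort.** Assume 30 De Novo participants averaging 0.9 year, about 27 participant-years. One event gives 3.7 per 100, exact 95% CI 0.09 to 20.6.

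**The case against.** A reader might infer that the plan expects 41% attrition and that its primary analysis therefore understates one-year risks. The documents do not support that. The figures 170 and 100 are both floors, and no dropout rate is stated. The Protocol Amendment 2 summary attributes the rise from 140 to 170 to the new De Novo cohort, not to dropout. The percentages are nowhere called one-year risks: as the share of treated participants reporting an event, they are correct. There is no control arm, so no treatment contrast is biased. With the post-dose window included, the shortfall can vanish near 85% retention. All of this stands.

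It can also be said that the context is already planned: disposition and discontinuation reasons by cohort (SAP 5.2), 15 exposure-duration thresholds plus participant-years (SAP 5.4.1), and the onset-interval table (SAP 5.4.3). This stands in part. It lets a reader see differential retention, but it does not put it into the AE results. The onset-interval table covers only treatment-related events and has no at-risk denominators.

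A further tempting reading is that rates would make chronic and episodic migraine comparable. They would not. Completers come through a placebo or atogepant lead-in without an AE judged an unacceptable risk (SAP 5.2; Protocol 4.3.2), while De Novo participants must be atogepant-naive (Protocol 4.4.2).

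Finally, SAP 1 places table specifications in a separate document that is not available here. A rate could be planned there, but the SAP does not call for one.

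**Conclusion.** The point holds as a cheap improvement, not as an error in the planned percentages. The TEAE tables ignore time at risk although safety over 52 weeks is the primary objective and the results are shown by cohort. For a true 10% one-year risk under constant hazards, the expected shortfall is about 14% to 22% in relative terms at the largest loss the plan tolerates, and 0% to 8% at 85% retention. The range within each depends on whether the event hazard persists after the last dose. Early dropout makes the shortfall larger; late dropout or front-loaded events make it small. Actual retention is not knowable from the documents.

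**What to change.** Keep the crude percentages. In SAP 5.4.3 add beside them the number of participants with an event per 100 participant-years at risk, with exact Poisson 95% CI, by cohort and overall, for:

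- any TEAE;
- TESAEs;
- TEAEs leading to discontinuation;
- AESIs;
- preferred terms at or above 5%.

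Define time at risk from first open-label dose to first event or, without an event, to the end of the TEAE window (30 days after last dose or Visit 15, whichever is later). Do not reuse the SAP 5.4.1 participant-years. In the onset-interval table, use the number at risk at the start of each interval as the denominator.

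Cost: no new data and no change to conduct, but a separate time-at-risk derivation for each event category, from dose, onset and visit dates already needed to define TEAEs. The rate assumes a roughly constant hazard, so it should be read with the onset-interval table. In the De Novo EM cohort the intervals will be too wide to support much, and a note should say that the CM versus EM contrast remains non-comparable for reasons other than retention.

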### 5.4.2. Treatment Compliance

Dosing compliance for the open-label treatment period is defined as the total number of open-label study treatments actually taken by a participant during that period divided by the number of open-label study treatments that were expected to be taken by a participant during the same period multiplied by 100. The total number of tablets actually taken during a specific period will be calculated from the study treatment record. Descriptive statistics for treatment compliance together with the compliance categories (< 80%, 80% - 120%, > 120%) will be summarized for

open-label study treatment period between 2 consecutive visits, as well as for the whole open-label treatment period of the study based on the Safety population.

